In the feasibility study, 4 sites will conduct the procedures outlined in this protocol. Procedures have been designed by the TELE protocol group and approved by the Clinical Trials Network (CTN) Steering Committee. The feasibility study will include 360 randomized participants—180 per treatment condition. Each of the sites is expected to randomly assign 60 to 120 participants. If the study shows that it is feasible to deliver the telephone calling intervention and to collect adequate data to compare with a control group, and there is evidence to suggest positive effects of the intervention, recommendations will be made to the CTN Steering Committee for a large-scale trial evaluating the efficacy of the TELE procedure.

The feasibility study will be conducted as follows:

Candidates eligible for randomization will include men and women enrolled in residential substance abuse treatment programs for at least 7 days but no more than 42 days. Participants must be at least 18 years of age and have the ability to understand and provide written informed consent. In addition, they must have been voluntarily admitted (not civilly committed) to the rehabilitation regimen (not admitted for detoxification only) and have a diagnosis for substance abuse or dependence as determined by residential program admission information. Referrals must be from a program servicing the targeted counties at the time of admission, and participants must plan to return to residence in the target counties after their discharge from the residential treatment program. Participants must have no evidence of current suicide intention or recent (\leq 30 days prior to admission) suicide attempt and must complete study requirements prior to departure from the program. All participants must have a working telephone number for contact after their discharge.

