11.3 HIV Risk Behaviors Survey

The Risk Behavior Survey (RBS), an abbreviated version of the Risk Behavior Assessment (RBA) developed by NIDA for the Cooperative Agreement, will be used to measure risk behaviors related to human immunodeficiency virus (HIV) and hepatitis C virus (HCV). Risk behaviors in the areas of drug use and sex in the previous 30 days are measured. Reliability and validity assessments of the RBS support its adequacy as a research tool for populations of drug users, including intravenous drug users (Darke et al., 1991; Weatherby et al., 1994; Needle et al., 1995).

11.4 CTN Addiction Severity Index-Lite Version 1 and Follow-up Version 1

The CTN Addiction Severity Index-Lite Version 1 and Follow-up Version 1 forms are multidimensional, semi-structured, comprehensive clinical interviews, which provide clinical information important for formulating treatment plans, as well as problem severity profiles in 6 domains commonly affected in substance abusers (McLellan et al., 1985). The domains covered are chemical abuse (alcohol and drug), medical, psychiatric, legal, family/social relations, and employment/support status. Composite scores for each problem domain are derived mathematically and used as change measures or outcome indicators as a function of treatment intervention.

These instruments also provide clinically necessary information on whether the participant is at imminent risk for suicide, thus permitting evaluators to implement any

needed immediate and/or early intervention strategies. The CTN ASI - Lite forms will be administered by a research staff member with a bachelor's degree in the social sciences or equivalent training and experience, as determined by the site's investigator. Composite scores will be calculated according to the procedures described by McGahan et al. (1982), and Carroll et al. (1994).

The CTN ASI - Lite Version 1 form will be administered during the baseline assessment and the CTN ASI - Lite Follow-up Version 1 will be administered at the 13-week follow-up visit.

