Equality of treatment groups at baseline will be evaluated by comparing demographic and drug-use information collected on the CTN ASI-Lite Version 1 and Follow-up forms. Baseline demographic values that potentially affect the responses or are found to be unevenly distributed between groups at baseline despite randomization may be investigated in supplementary analyses. Baseline values are not planned to be covariates in any analyses because sample sizes are expected to be too small. Where possible, treatment effects will be summarized by gender, ethnicity, and age group separately.

A summary will be prepared to show dropouts/retention over time in each treatment group. The number of missing observations will be compared between treatments. In the analysis of the effect of the telephone call regimen on the participant abstinence (objective measure by urinalysis & breathalyzer), participants lost to follow-up at 13 weeks will be handled in 2 different approaches in an attempt to elucidate the influence of missing data on interpretation of the results. In the first analysis, participants lost to follow-up at 13 weeks will be considered "non-abstinent" to account for the possibility that non-abstinent participants may be more likely to be lost at follow-up. In the second approach, participants lost to follow-up at 13 weeks will be considered as missing. We anticipate that the category "missing at follow up" will account for 20% or fewer of randomized participants. Effects of gender and substance use diagnosis will be investigated in a supplementary analysis.

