13.5 Sample Size Estimate

Because this is a feasibility study, we had 3 major considerations: to complete the study in a timely manner, to keep the costs low, and to recruit as many participants as possible within these constraints. Thus, rather than statistical power guiding the sample size decision, real-life research constraints were invoked. In terms of study timeline, the duration of enrollment is anticipated to be 9–12 months in order to give the CTPs ample time to become familiar and competent with the study protocol, so that in addition to

months reflecting start-up, we would have data for several months that reflect the full potential of the CTPs to recruit participants. Each CTP is expected to randomize about 60 to 120 participants across the recruitment period. Thus, 360 participants are estimated for the total sample size across CTPs.

Not all individuals who agree to participate will complete their residential treatment episode, and an additional number will fail to meet the eligibility criteria for the study. Based upon program experience, we expect approximately 25% of participants to fail to complete their residential treatment, and an additional 15% to fail to meet the eligibility criteria of the study. Thus, if 16 participants per month agree to participate, we would expect 12 to complete their residential treatment, and approximately 10 to meet the eligibility criteria of the study. Based on these numbers, we expect that approximately 4 participants per week will agree to participate at each CTP (at intake to the residential program).

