13.6 Post Hoc Analysis

During the course of conducting the primary and secondary summaries, the data may suggest other interesting differences by CTP or treatment group. Post hoc analyses are anticipated to explore these findings. One potential post hoc analysis would be the exploration of factors found to be significantly different between groups at baseline, as they relate to study outcomes. Other potential post hoc analyses would be the exploration of the effects of gender and site on outcomes. Additionally, a comparison of baseline characteristics between participants who are randomized and those contacted for follow-up will be completed for generalization of the conclusions.

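### Sample size is given as the reason for planning no baseline covariates in any analysis, but the planned sample supports a small adjusted model for the pooled comparisons

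*Protocol*

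**What the plan says.** Section 13.3.1 of the protocol names unadjusted methods for the efficacy outcomes: tests for a difference in proportions, the t-test, and the Wilcoxon rank-sum test if normality fails. It then says: "Baseline values are not planned to be covariates in any analyses because sample sizes are expected to be too small". No other reason is given, and the sentence covers every analysis.

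The other relevant statements are:

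- **Size.** Section 3.0: "The feasibility study will include 360 randomized participants—180 per treatment condition". Section 13.3.1 expects 20% or fewer to be missing at follow-up. Section 13.5: "Each CTP is expected to randomize about 60 to 120 participants across the recruitment period", with four sites.
- **Baseline data.** Section 11.4: "The CTN ASI - Lite Version 1 form will be administered during the baseline assessment". Its follow-up version is given at week 13. Table 3 shows the Risk Behavior Survey at both times, and the urine screen, breath test and continuing care form at follow-up only.
- **Outcome hierarchy.** Section 13.3 makes engagement, urine result and breath result the main efficacy measures. ASI-Lite and Risk Behavior Survey outcomes are supplemental.
- **What is left open.** Section 13.3.1 allows supplementary analyses of demographic factors that might influence outcome or that turn out unbalanced, and of gender and substance use diagnosis. Section 13.6 offers, as one possible post hoc analysis, "exploration of factors found to be significantly different between groups at baseline, as they relate to study outcomes".
- **Purpose.** Section 5.1 lists the magnitude of the effect size among the critical feasibility aspects. Section 13.3.1 says that the efficacy results will inform the sample size of a later trial.

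**The concern.** The reason looks wrong on the protocol's own figures, because several hundred participants are ample for a handful of covariates. It also fits poorly with its surroundings. Section 13.3.1 plans treatment effects separately by gender, ethnicity and age group, and comparisons within each site. Both divide the sample, which costs far more precision than adding one covariate to a pooled model.

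The precision of the effect estimate is at stake, since that estimate is to be carried into the design of the next trial. What remains in place of a prespecified adjustment is supplementary or post hoc work. One suggested trigger for it is a significant baseline difference. Under randomization such a difference arises by chance, and selecting on it picks covariates after seeing the data and by imbalance, not by how well they predict outcome.

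A statistical analysis plan written to follow this protocol would inherit the sentence, so the point does not simply pass to that document.

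**Working it through.** **1. The planned sample size.** The protocol sets no power, significance level or effect size. Its 360 follows from accrual: section 13.5 expects "approximately 10 to meet the eligibility criteria of the study" per month at a site, and "the duration of enrollment is anticipated to be 9–12 months".

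- 10 per month × 9 months × 4 sites = 360.
- Equivalently, 4 sites × 90 (the midpoint of 60 to 120) = 360.
- At 20% loss: 0.80 × 360 = 288 seen, or 144 per arm.

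**2. Cost of adjustment if the covariates predict nothing.** For a linear model with k covariates besides arm, the ratio of adjusted to unadjusted variance of the treatment effect is

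(1 − R²) × (N − 3) / (N − k − 3).

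Arm, three site terms and one baseline value give k = 4. With R² = 0:

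| N | k = 4 | k = 5 | k = 10 |
|---|---|---|---|
| 360 | 357/353 = 1.011 | 357/352 = 1.014 | 357/347 = 1.029 |
| 288 | 285/281 = 1.014 | 285/280 = 1.018 | 285/275 = 1.036 |

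The penalty for the proposed model is 1.1% to 1.4%. Five covariates break even at R² = 5/357 = 0.014 (N = 360) or 5/285 = 0.018 (N = 288). If every site reached only its lower limit, 4 × 60 = 240 randomized and 192 seen, the k = 4 penalty would be 189/185 = 1.022.

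**3. Binary abstinence.** The protocol gives no abstinence rate. Assume that the rarer outcome has a rate of 20% to 50%. Then 288 observed gives 58 to 144 such outcomes, enough for about 5 to 14 covariates at the customary 10 per covariate. At an assumed 10% there are 29, enough for about 2.

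**4. Possible gain for ASI-Lite and Risk Behavior Survey outcomes.** These exist only for participants seen, so N = 288 applies. The correlation r between baseline and week 13 is not given; 0.3 to 0.6 is an assumption. Adjustment multiplies the variance by 1 − r²:

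- r = 0.3: factor 0.91. 288/0.91 = 316, equivalent to 28 extra participants.
- r = 0.5: factor 0.75. 288/0.75 = 384, equivalent to 96.
- r = 0.6: factor 0.64. 288/0.64 = 450, equivalent to 162.

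The 95% half-width for a standardized difference is 1.96 × √(2/144) = 0.23 unadjusted, and 0.23 × √0.75 = 0.20 at r = 0.5. Charging the 1.4% from step 2 changes the factors 0.91 and 0.64 only to 0.92 and 0.65.

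**5. Possible gain for the main measures.** Engagement, urine and breath results have no baseline counterpart, so step 4 does not apply to them. A simulation compared the unadjusted risk difference with one standardized from a logistic model. It used N = 288, 2,000 runs per setting, and five covariates of which at most one was prognostic. The variance ratio was 1.02 with no prognostic covariate, 0.96 with log-odds 0.5 per SD, and 0.85 with log-odds 1.0 per SD. All three strengths are assumed.

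**6. Within one site.** At N = 60, one covariate costs 57/56 = 1.018 and five cost 57/52 = 1.096. With 48 seen (20% loss), five cost 45/40 = 1.125.

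**The case against.** The strongest reply has four parts.

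- **The plan is less restrictive than the sentence suggests.** A reader might infer that baseline factors are shut out altogether, or that they can enter only through chance imbalance. The documents do not support that. Covariates are described as not planned. Supplementary analyses may address demographic factors thought to affect outcome, which is a prognostic criterion, as well as gender and diagnosis. The significance trigger in section 13.6 is only one suggestion. This stands, though none of that work is a prespecified adjusted estimate.
- **Small numbers do matter somewhere.** Comparisons are planned within sites of perhaps 60 randomized, where several covariates cost about 10% of variance. This stands for within-site work and for a rare binary outcome. The sentence is not limited to those cases.
- **The loss is unproven.** A reader might infer that precision is certainly discarded, or apply step 4 to all 360 and to all outcomes. The first needs correlations that the protocol does not give. On the second, 360/0.91 and 360/0.64 would suggest about 36 to 202 extra participants, but the protocol states no imputation for these outcomes and the main measures have no baseline value.
- **The consequence is limited.** Unadjusted comparisons are valid under randomization. Efficacy is secondary and exploratory with no significance level, and the planned raw proportions, means and SDs are themselves useful for a future sample size. This stands, and it is why the unadjusted results should be kept.

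**Conclusion.** The point holds in limited form. As a reason for having no baseline covariates in the pooled comparisons, small sample size is contradicted by the planned 360 randomized and at least 288 seen. The proposed model costs at most about 1.4% of variance at those sizes, given the protocol's own ceiling of 20% loss.

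The benefit forgone is possible rather than established. It is about 9% to 36% of variance for the supplemental ASI-Lite and Risk Behavior Survey outcomes if r lies between 0.3 and 0.6. For engagement and abstinence it is likely smaller and could be nil. The documents do not support a claim of bias, of invalid tests, or of a known loss on the main measures. The change is still worth making, because it costs almost nothing and serves the stated aim of estimating an effect size.

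**What to change.** In section 13.3.1, delete the sentence that rules out covariates on grounds of sample size. For the pooled analyses, prespecify an adjusted estimate beside each unadjusted one:

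- **ASI-Lite and Risk Behavior Survey outcomes:** ANCOVA with arm, site and the outcome's own baseline value.
- **Abstinence:** a model with arm, site and baseline ASI-Lite drug or alcohol use, reported as a standardized risk difference with 95% CI. A conditional odds ratio would not show the precision gain as a smaller standard error.
- **Engagement:** the same covariates, reported as a mean difference with 95% CI.

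Site belongs in each model because randomization is stratified by it. Keep within-site comparisons unadjusted or limited to one covariate. In section 13.6, do not use baseline significance tests to choose covariates.

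The cost is one paragraph of text and slightly more analysis, with a worst-case variance penalty under 2% at the planned size. No new data are needed.

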5.0 STUDY OBJECTIVES

5.1 Feasibility

The primary objective of this clinical investigation is to evaluate the feasibility of a randomized clinical trial testing the use of a telephone call support (TELE) procedure to enhance continuing care activities after completion of residential treatment programs for substance abuse. Several aspects of this feasibility study are equally important and failure to complete them would indicate the need for serious reconsideration or restructuring of a future full-scale TELE protocol. The critical aspects of feasibility in this study are listed below:

- 1. Determining the proportion of the total eligible participants who volunteer to participate in the study
- 2. Obtaining informed consent on an adequate number of newly admitted residential treatment patients for participation in the study
- 3. Determining the proportion of consented participants who complete all required residential treatment and data collection activities and are randomized into one of the 2 study conditions
- 4. Determining whether it is possible to contact this population via telephone after they have been discharged from residential substance abuse care
- 5. Determining how many of the 7 scheduled calls in the group randomized to the TCG actually have the intervention delivered
- 6. Determining whether counselors who deliver the calls can be trained to conduct these calls in a standardized manner using a structured "script"
- 7. Determining the magnitude of the "effect size" within such a design (This information will be needed in power calculations for any future study.)
- 8. Determining whether adequate data (i.e., sufficient and equivalent follow-up data), which would be required in an adequately powered multi-site trial, are collectible in typical community-based treatment organizations after participants leave the treatment setting

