10.4 Intervention after Discharge

Following discharge, a total of 7 telephone contacts at weeks 1, 2, 4, 6, 8, 10, and 12 will be made by the TELE counselor to all participants randomly assigned to the TCG. Each contact will follow the scripted procedure outlined in the Counselors Manual. The same procedure will be followed upon each contact. Up to 3 attempts will be made to contact the participant for each of the 7 scheduled calls, regardless of the outcome of the previously scheduled call.

Unless consent to participate is expressly revoked by the individual, he or she will continue to be contacted as scheduled. Attempts to contact the participant and the outcome of the call will be recorded on the participant contact form in the CRF. The SCG participants will not be contacted by the TELE counselor following their pre-discharge session.

A portion of calls will be recorded and at least 10% of successful calls will be randomly selected and scored for fidelity to the intended call procedures. Each node supervisor will provide supervision to the TELE counselor, per standard practice for the particular program.

In order to provide standardization across all TCG calls, the TELE Counselors Manual provides directions for conducting these calls. Information obtained during the course of the call will not be used as research data with the exception of serious adverse events. These events disclosed by the participant will be documented and reported as described in section 12.0.

The manual also provides minimal instructions for handling medical emergencies such as suicidal threats. Each facility is expected to have a written plan in place for emergency situations. If a plan is not in place, a procedure will be developed by the facility and should be available for review by the node quality assurance (QA) monitor prior to enrollment. Each facility has the responsibility for training its research staff on the facility's emergency plan.

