13.7 Randomization

Randomization (1:1 treatment allocation) will be performed using a randomized block design, stratified by site. This will enable sites to enroll differing numbers of participants while maintaining a fairly close balance between groups within sites. One of the outcomes of this feasibility study is the measure of whether the CTPs are capable of enrolling the expected numbers. Thus, some of the CTPs may not enroll the expected number, and we will employ blocking in order to preserve our ability to examine existent data at the end of the study. Block size will be determined by the statistical group at the Lead Node who will prepare the randomization scheme.

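### With calls to one arm only, the two planned ways of handling loss to follow-up need not bracket the true abstinence difference, and the protocol names no arm-specific sensitivity analysis

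*Protocol*

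**What the plan says.** Protocol section 13.3.1 sets out two analyses of objectively measured abstinence at week 13. The first counts everyone lost to follow-up as non-abstinent, and the only reason given is "to account for the possibility that non-abstinent participants may be more likely to be lost at follow-up". The other is stated as "In the second approach, participants lost to follow-up at 13 weeks will be considered as missing". The same section compares binary outcomes with a test of proportions and plans no baseline covariates, so the second approach is a complete-case comparison. The pair is meant to show how missing data affect interpretation. The section expects 20% or fewer to be missing, gives no split by arm, and will compare the number missing between arms.

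Staff contact after discharge differs by design. TCG has seven scheduled calls with up to three attempts each (section 10.4), the last on days 81–87. The visit window opens on day 88 (Table 1). For the other arm, "The SCG participants will not be contacted by the TELE counselor following their pre-discharge session". Section 5.1 leaves open whether "sufficient and equivalent follow-up data" can be obtained. It also lists the effect size as a critical feasibility aim.

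**The concern.** Calls that run almost to the opening of the visit window may make TCG participants easier to find. If so, loss will be lower in TCG, and a rule that scores every loss as a failure turns part of that gap into an apparent abstinence difference. Complete-case analysis does not reliably correct this, because it is biased when loss is related to substance use. Nothing in section 13.3.1 varies the assumption about the lost by arm, although arm is where a difference is most plausible.

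What is at stake is the estimate more than any P value. Sections 13.2 and 13.3.1 pass the efficacy results to the effect size and sample size of a full-scale trial. A distorted abstinence difference could leave that trial too small, or weaken or inflate the case for running it.

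**Working it through.** **The plan's own figure.** "The feasibility study will include 360 randomized participants—180 per treatment condition", and 2 × 180 = 360. Section 13.5 supports the total: "if 16 participants per month agree to participate, we would expect 12 to complete their residential treatment, and approximately 10 to meet the eligibility criteria", and 10 per month × 9 months × 4 sites = 360. It is also 4 × 90, the midpoint of the 60–120 range per site. The 20% ceiling on missing data is 0.20 × 360 = 72 participants. It has no derivation to reproduce.

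**Inputs from the protocol.** 180 per arm; 1:1 allocation (section 13.7); two-sided test of two proportions; up to 20% lost overall.

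**Assumptions, not in the protocol.** True abstinence is 50% in both arms, so the true difference is zero. Loss is 15% in TCG (27 of 180) and 25% in SCG (45 of 180), together 72 participants, which is the 20% ceiling. A 0.05 level is used for illustration only, because the protocol sets none.

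**Formulas.** Let m be the share lost, q the true abstinence rate among the lost and r the rate among those seen; T is TCG and S is SCG. Differences are TCG minus SCG.

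- Lost counted as non-abstinent: bias = mS·qS − mT·qT.
- Complete-case: bias = mT(rT − qT) − mS(rS − qS), with r = (0.50 − m·q)/(1 − m).

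Two worked cases:

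- q = 25% in both arms: 0.25 × 0.25 − 0.15 × 0.25 = +0.025.
- qT = 10%, qS = 40%: 0.25 × 0.40 − 0.15 × 0.10 = +0.085. Complete-case gives 0.485/0.85 − 0.400/0.75 = +0.037.

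**Results at 15% and 25% loss** (percent abstinent TCG v SCG; difference in points, computed before rounding):

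| q TCG | q SCG | Lost = non-abstinent | Complete-case |
|---|---|---|---|
| 0% | 0% | 50.0 v 50.0; 0.0 | 58.8 v 66.7; −7.8 |
| 25% | 25% | 46.25 v 43.75; +2.5 | 54.4 v 58.3; −3.9 |
| 50% | 50% | 42.5 v 37.5; +5.0 | 50.0 v 50.0; 0.0 |
| 60% | 60% | 41.0 v 35.0; +6.0 | 48.2 v 46.7; +1.6 |
| 10% | 40% | 48.5 v 40.0; +8.5 | 57.1 v 53.3; +3.7 |
| 40% | 10% | 44.0 v 47.5; −3.5 | 51.8 v 63.3; −11.6 |
| 25% | 15% | 46.25 v 46.25; 0.0 | 54.4 v 61.7; −7.3 |

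With a common q, the first rule's bias is q(mS − mT), whatever the true abstinence rate. At q = 50% it is +2.0 points for 18% v 22% loss and +10.0 points for 10% v 30%.

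**Scale against sampling error.** For 42.5% v 37.5%, the pooled standard error is √(2 × 0.40 × 0.60/180) = 0.052, so a 5-point bias is about one standard error. The chance of P < 0.05 in favour of TCG would be 16% instead of 2.5%. At q = 25% it is 6.9%, and at 10% v 30% loss with q = 50% it is 49%.

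**The case against.** A reader might infer that the first rule favours TCG whenever the calls improve follow-up, or that the two analyses never bracket the truth. The documents and the arithmetic support neither. The bias is zero if all the lost are non-abstinent, the limiting case of the protocol's own rationale. It reverses at 15% and 25% loss once qT exceeds 25/15 = 1.67 times qS. With no true effect, a common q and the lost doing no better than average, the pair does bracket zero. At q = 50%, complete-case is unbiased, so the two analyses would disagree and expose the artefact. The protocol never claims that the pair brackets the truth.

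Better follow-up in TCG is plausible but not established. Both arms get the pre-discharge meetings, an attempt to schedule the visit, an appointment card and research-assistant contact details (section 10.3.1), and locator updates are taken in both (section 10.5). Retention and missing counts will be shown by arm (section 13.3.1). Those randomized will be compared at baseline with those contacted for follow-up (section 13.6). The tests are exploratory, and section 13.2 draws the effect size from several analyses. A statistical analysis plan, not at hand, could add further sensitivity analyses.

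Most of this stands and limits the point. It does not remove it: counts of missing data reveal an imbalance but not how far it moves the estimate, and an exploratory label does not protect a point estimate that will be reused.

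**Conclusion.** The concern holds in a limited form. The two analyses need not bracket the true difference when abstinence among the lost differs by arm, and they can then err together in either direction: +8.5 and +3.7 points, or −3.5 and −11.6, with no true effect. They also both lean to TCG if the lost do better than average (+6.0 and +1.6), although that runs against the protocol's rationale. Under lower TCG loss and a similar non-zero q in both arms, the first rule alone leans to TCG, by 2.5 to 5.0 points at q = 25% to 50% and 15% v 25% loss.

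The loss split, the 50% abstinence rate and every q are assumptions, so neither the size nor the direction of any bias in this trial is established. This is a cheap improvement that helps the plan meet its aim of showing the influence of missing data. It is not a flaw that invalidates the analysis.

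**What to change.** Keep both planned analyses. Add to section 13.3.1 a two-way tipping-point table that varies the assumed abstinence rate among the lost from 0% to 100%, separately for TCG and SCG, with the treatment difference in each cell. Counting all the lost as non-abstinent is the 0%/0% cell. The complete-case estimate is the point where each arm's lost are given that arm's observed rate. Report loss by arm beside each estimate. When the effect size is carried to the full-scale trial, give the range over plausible cells and not a single imputed figure.

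Multiple imputation using site, baseline ASI-Lite scores and the attendance verified for missed visits (section 10.6.3) can be an optional further sensitivity analysis. It should not replace the main analysis. In its standard form it assumes that loss is explained by the variables used, so it would not by itself correct the cases where the lost differ by arm in unmeasured ways. The attendance data are also weaker for non-attenders, because releases for programs outside the care plan are signed only at the visit (section 10.6.2).

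The cost is a short wording change, a little extra analysis and a wider stated range. No new data are needed.
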